2.6 Step 6, Pilot Testing

In this step, we will implement the program evaluation plan established in Step 5, and will also include a pilot outcome evaluation to estimate the impact of the beta-RC on function and quality of life. We will implement and evaluate the beta-RC using a mixed method, single group study with a convenience sample of approximately 35 HNC survivors post primary cancer treatment, *recruited from the Princess*

*Margaret Cancer Center HNC clinics**, with inclusion and exclusion criteria and recruitment as described above in section 2.4.1. The procedures will be as described above in 2.4.1.2, with the following changes:

- a) An additional research assessment (Session 4) will be added. Session 4 will occur 1-2 months after Session 3; the participant will complete a follow-up assessment with the research assistant (approximately 60 minutes), either as a face-to-face visit or as a telephone interview. The assessment battery will be based on the tools described in Table 2.
- b) The intervention will include revisions based on feedback and observations from the pre-testing stage. The pilot testing version (beta RC) of the previously described intervention can be found in Table 3.
- c) The intervention will continue to be video recorded and reviewed by an investigator for fidelity. This will occur for the first 3 participants and then for every 5th participant who completes the intervention, starting with the 1st (1,2,3, then 8th, 13th, and so on). To explore survivor experiences with the RC, a survey will be administered during session 3, based on one-on-one semi-structured interviews carried out during the pre-testing phase. (approximately 30 minutes). The survey is included in Appendix B.

Participants will be remunerated \$25 for each *research* visit to the site to offset their transportation and parking costs. Additional *intervention-only* visits will not have any remuneration.

Quantitative data analysis will be exploratory and descriptive, and effect sizes will be calculated for all outcomes to help plan for a future, controlled trial. We will calculate means, standard deviations, and Cohen's *d* [39] effect size for normally distributed data. For non-normally distributed data, we will calculate medians, ranges, and a nonparametric effect size *r* using the formula $r^2 = z^2 / N$. [40] For qualitative analysis, all interviews will be audio recorded, transcribed verbatim, and analyzed using a

* Note that Sunnybrook-Odette will not be involved with data collection in Step 6

Development and pilot evaluation of rehabilitation consult for survivors of head and neck cancer

two-phased, hybrid approach that is both deductive and inductive, described by Fereday and Muir-Cochrane [41]. Findings will be summarized and reported to the Advisory Panel, who will then make recommendations regarding any additional modifications to the RC. The research team will make final decisions about RC modifications and will finalize a version for future evaluation.

In order to further evaluate individual program components, and address the objectives of adoption and knowledge translation to rehabilitation professionals, the research team will evaluate the brief, head and neck specific, functional evaluation that was developed as part of the project, and described in section 2.4. Content validity will be assessed by collecting feedback from professionals in the multidisciplinary head and neck cancer site group, regarding the degree to which items of the functional assessment adequately represents relevant rehabilitation issues in the head and neck cancer population. Concurrent (convergent and divergent) validity will be assessed through comparing the results of the functional assessment to the standardized and validated FACT-H&N and SF 36 assessments, which are already being administered to study participants. Data will be analysed using the content validity index, descriptive statistics, and Spearman's rho correlation coefficients.

Assuming positive outcomes from this single group evaluation, a future, multi-site controlled trial will be designed and implemented in a future study. Results from this study will provide feasibility information, such as recruitment rates; help to define primary and secondary outcomes; and provide data to calculate sample size to ensure an adequately powered trial.

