At both the pre and post intervention research assessments, the following constructs will be evaluated: function, quality of life, self-efficacy, community participation, goal attainment, and return to work status (if applicable). Additionally, the research assistant will collect data on the time to complete the assessment battery; perceived respondent burden; and ease of use of all tools. At the post-intervention assessment, the participant will be asked to complete a survey related to the content and process of the alpha-RC. Table 2 describes all tools to be used. The rehabilitation consultant (CD) will video record the face-to-face phase and audio record the follow-up telephone call so that the processes can be reviewed and analysed in depth. The following information will be extracted from these recordings: time required for each segment in the process; adherence to planned methods and theory; challenges and successes with each participant.

Descriptive analysis will be conducted; the research team will review results, and then make decisions about adaptations to the alpha-RC and finalization of the outcome measure battery. The alpha-RC will

be modified iteratively based on the information gleaned from each survivor, outcome data, and feedback from research team members. Step 4 will be considered complete when the investigators are satisfied that a version of the RC suitable for formal pilot evaluation has been developed, the beta-RC.

2.5 Step 5: Planning for adoption, implementation, and sustainability.

This is a planning step, in which a logic model will be developed to guide the initial implementation and program evaluation. Specific objectives for adoption, implementation, and sustainability will be established, and determinants of those will be considered. We will seek input on the logic model from the Advisory Panel.

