Self-Efficacy	HNC RC Self-Efficacy Tool	There was no existing tool which adequately measured self-efficacy as it relates to the goals of this study. Therefore, a self-efficacy tool was created, using a 0-100 rating scale, based on Bandura (2006) "Guide to Constructing Self-Efficacy Tools" to measure the confidence of participants to achieve outcomes specific to this study. This tool is included as Appendix D.
Return to Work	Radiation Therapy Oncology Group (RTOG) Work Status Questionnaire [47]	The RTOG Work Status Questionnaire is a brief, patient-report tool that takes less than 5 minutes to complete. It was designed for use in RTOG trials, and psychometric properties have not been tested, but meets content validity criteria and sensibility criteria.
Goal Attainment	Goal Attainment Tool	Participants are asked about how well they currently perform a stated goal, which they develop in consultation with the rehabilitation consultant, how satisfied they are with this performance, and their confidence they can do the goal, and rate these on a scale of 0-100. A score of 0 represents low performance/satisfaction, and 100 represents the highest level of performance/satisfaction. This tool is included as Appendix C.
Patient Perspective Intervention Process	Rehab Consult Process Survey	Items for this survey were derived from questions posed in interview format during an earlier testing phase. 17 statements are scored using a 3-point Likert-type scale. Statements concerns intervention process issues such as timing, ease of use, and value of specific consult segments. This can be found in Appendix B.

Table 3: Pilot (beta) testing version of Rehabilitation Consult Process

Name	Process Steps	Methods
Orientation	A. A brief orientation (Appendix A) is given by the rehab consultant to orient the survivor to the reason for the consultation and the process.	Advance Organizer
Consultation	B. The rehab consultant reviews the brief HNC-specific functional evaluation (BRASH), and then consults with the survivor regarding the results. The survivor identifies the issues that are currently most important to him or her. If the participant has no goals, the rehabilitation closes the session by reinforcing that the options available if he/she has issues arising at a later time, and providing information on accessing the resource compendium.	Goal-setting Individualization Therapeutic alliance Facilitation Participatory problem solving

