Goal-setting	C. The survivor and the rehab consultant work collaboratively to make goal statements based on issues identified by the survivor as most important to him or her. The rehab consultant administers a goal attainment tool (Appendix D) wherein the participant rates his or her current performance, satisfaction, and confidence with the goals.	Goal-setting Individualization Therapeutic alliance Facilitation Participatory problem solving Cognitive strategy training
Teach cognitive strategy	D. The rehab consultant teaches the global problem solving strategy, Goal-Plan-Do-Check (Meichenbaum, 1971).	
Action Planning, Planning Coping Responses, and Introduction to Resources	E. Using the Goal-Plan phases of the problem solving strategy, the rehab consultant and the survivor develop an action plan to meet the identified goals. The rehab consultant uses motivational interviewing techniques (eliciting change talk, evoking motivation to make positive changes (Miller & Rollnick, 1991) and guided	Individualization Therapeutic alliance Facilitation Participatory problem solving Motivational interviewing techniques Framing Guided discovery Implementation intentions Planning coping responses

	
discovery techniques (ask don't tell, coach don't adjust, make it obvious, and one thing at a time (Polatajko & Mandich, 2004)). The rehab consultant reviews the rehabilitation resources of which the survivor may already be aware, or accessing. The rehab consultant reviews the study website (resource compendium) (www.hncrehab.ca), with the survivor, for future use, and facilitates the assembly of resources previously unknown to the survivor, which are necessary to implement the survivor's plans. Also as part of the planning process, the survivor identifies potential barriers to implementing the action plan and develops coping responses, using planning coping responses techniques (Marlatt & Donovan, 2005), all facilitated by the rehabilitation consultant.
	Verbal persuasion
Execution	
F. Facilitated by the rehab consultant, the survivor reviews his or her goals and action plan for clarity, and is encouraged to execute (do) his or her plan. Follow-up appointment is scheduled for between 2 and 10 weeks later, at a mutually convenient time. This may be in person, or via telephone, as per survivor's preference.
	Implementation intentions Planning coping responses
Follow-Up Process		

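### After the first 3 participants, fidelity review in the pilot is limited to completers, so delivery to later non-completers can never be examined and the rule cannot say which Session 1 to record

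*Combined protocol and SAP*

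**What the plan says.** Section 2.6 plans a "single group study with a convenience sample of approximately 35 HNC survivors post primary cancer treatment". Its procedures are those of 2.4.1.2 apart from listed changes. Item c) of those changes deals with fidelity:

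- "The intervention will continue to be video recorded and reviewed by an investigator for fidelity".
- The opening 3 cases are covered without an explicit condition; after them, the rule takes "every 5th participant who completes the intervention, starting with the 1st (1,2,3, then 8th, 13th, and so on".

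Three other places bear on how this works:

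- Section 2.4.1.2, carried into the pilot by reference, says the rehabilitation consultant "will video record the face-to-face phase and audio record the follow-up telephone call". The recordings are to yield segment times, adherence to the planned methods and theory, and the challenges and successes met with each participant.
- Table 3, Execution row: "Follow-up appointment is scheduled for between 2 and 10 weeks later".
- Table 3, Consultation row: "If the participant has no goals, the rehabilitation closes the session", with information on how to get help later.

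The documents do not define completion. They do not say whether positions are counted by enrolment or by completion, or whether all sessions are recorded and only some reviewed. They give no fidelity score, no threshold and no expected completion rate.

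**The concern.** The session that most needs a fidelity check is the face-to-face one, where goals are set, the problem-solving strategy is taught and the action plan is made. Whether that session can be reviewed depends, after the first 3 participants, on something that happens weeks later. That is selection on an outcome which delivery itself might influence.

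Two things are at stake. First, if a session went badly and the participant did not return, its recording falls outside the review. The pilot then cannot say whether delivery had any part in the loss. Second, the rule may not be workable. If only the sessions due for review are recorded, nobody can know on the day of Session 1 whether that participant will turn out to be the 8th or 13th completer.

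Item c) is the only fidelity check described for the pilot. Section 2.6 has the findings go to the Advisory Panel before the intervention is finalised for a future controlled trial.

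**Working it through.** **1. The plan's own sequence.** Taking the first 3 and then every 5th counted from the 3rd gives 1, 2, 3, 8, 13, 18, 23, 28, 33. This matches the listed order and makes 9 reviews if 35 complete (9/35 = 26%). Counting every 5th from the 1st would add 6, 11, 16 and so on, which does not match; the total for 35 is again 9.

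**2. Who can be reviewed.** The documents give no completion rate, so 80% is assumed for illustration. Then 28 of 35 complete and 7 do not. Applied to 28 completers, the rule reaches positions 1, 2, 3, 8, 13, 18, 23, 28, which is 8 reviews. If the first 3 participants are among the completers, 0 of the 7 non-completers can be reviewed. At an assumed 90% (32 completers) it is again 8 reviews, and 0 of 3 non-completers. The workload barely changes; what changes is who is eligible.

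**3. When the position is known.** Follow-up falls 2 to 10 weeks after Session 1, a window of 10 - 2 = 8 weeks. Section 2.4.1.1 anticipates 1 recruit per week, and 2.6 carries that recruitment approach forward. At that rate, order by completion can differ from order by Session 1 by up to about 8 places, more than the step of 5. So if positions are counted by completion, they cannot be assigned at Session 1.

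**4. Could the review mislead, and in which direction?** Suppose fidelity were scored from 0 to 100. Let c be the completion proportion, g the shortfall in fidelity among non-completers, e the shortfall in the first 3 cases while delivery settles, and k the number reviewed. Assume the first 3 complete. Then

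bias = (1 - c) × g - (3/k - 3/35) × e.

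The first term overstates fidelity. The second understates it, because the earliest cases are over-represented: 3/9 = 33% of reviews against 3/35 = 9% of participants when k = 9. With c = 28/35 and k = 8, the bias in points is:

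| g | e = 0 | e = 10 | e = 20 |
|---|---|---|---|
| 0 | 0.0 | -2.9 | -5.8 |
| 10 | +2.0 | -0.9 | -3.8 |
| 20 | +4.0 | +1.1 | -1.8 |

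For example, with g = 20 and e = 20: 0.20 × 20 - (0.375 - 0.0857) × 20 = 4.0 - 5.8 = -1.8. All values of c, g and e are assumptions. The sign is not determined.

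**5. Effect of ordering by Session 1.** The positions up to 35 remain the same 9. With 7 non-completers among the 32 participants after the first 3, the 6 later positions would include on average 6 × 7/32 = 1.3 of them, if position is unrelated to completion. Under the present rule that number is 0.

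**The case against.** The strongest reply is that this is an exploratory, descriptive, single-group pilot in which fidelity review is a process check with no estimate attached. No document links drop-out to poor delivery, and 2.4.1.2 notes that many patients travel from out of region, which is a reason to miss visits that has nothing to do with delivery. Closing a session when there are no goals is a planned step in Table 3 and may count as completing. The list of what the pilot supplies to the future trial does not name fidelity. All of this stands, and it limits how serious the point is.

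Four stronger readings are tempting, and the documents do not support them:

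- A reader might infer that the whole review sample consists of completers. The condition is attached to the every-5th group and not clearly to the first 3, who are a third of 9 reviews.
- A reader might call the rule self-contradictory. The phrase about starting with the 1st is loose, but the listed order settles what is meant.
- A reader might infer that reported fidelity will be too high. No score, completion rate or fidelity gap is given, and the weight on early cases can push the other way.
- A reader might infer that the consultant can foresee every reviewed session. If positions are counted by completion, foresight at Session 1 is limited beyond the first 3. The documents do not say whether the consultant is told the rule.

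None of this restores the later non-completers to the review or tells staff which Session 1 to record.

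**Conclusion.** The point holds as a gap in coverage and workability. After the first 3 participants, those who stop or miss follow-up cannot be reviewed. Those whose session closes with no goals may also be excluded, depending on a definition the plan lacks. The review could miss delivery problems in these people and cannot show whether delivery contributed to drop-out. As written, the rule can select Session 1 recordings only if every Session 1 is recorded, which the plan does not clearly say.

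Bias in either direction remains possible, and the documents do not determine its size. The range of -5.8 to +4.0 points rests on 80% completion and shortfalls of 0 to 20 points, all assumed, and on a score the plan does not define. This should not hold up the pilot, but it should be corrected before enrolment, because a session that was not recorded cannot be reviewed later.

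**What to change.** In 2.6 c), delete the completion condition and the phrase about starting with the 1st. State instead: *Participants selected for fidelity review are the 1st, 2nd, 3rd, 8th, 13th and so on by date of Session 1, regardless of whether they go on to complete; whatever sessions were delivered to them are reviewed.* Also say whether all sessions are recorded or only those due for review. The revised rule works in either case, because the position is known when Session 1 is held.

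The cost is a short edit. The workload stays at 9 of 35. Some reviewed participants will have only a face-to-face session to review. With perhaps one or two non-completers among them, the review can describe delivery to such people but cannot support a formal comparison with completers.

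Optional addition, if sessions of all consenting participants are recorded: after the first 3, draw one participant at random from each following block of 5, including a final partial block, and do not tell the consultant beforehand. For 35 participants, 35 - 3 = 32 makes 6 full blocks and one of 2, so 3 + 7 = 10 reviews. This removes foreseeable positions. It means recording and storing sessions that are never reviewed, and if each draw waits until its block is recorded, feedback on drift comes later.

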2.4.1 Pre Testing

2.4.1.1 Participants and Recruitment Pretesting of the alpha-RC process will be conducted using an iterative single case series of 5 to 10 survivors of HNC. Participants will be recruited from the HNC clinics at Sunnybrook Odette Cancer Centre and Princess Margaret Cancer Centre. Eligibility criterion

Development and pilot evaluation of rehabilitation consult for survivors of head and neck cancer

are adult survivors of HNC who have completed active treatment (surgery, radiation, chemotherapy or any combination thereof) within the last year. Exclusion criteria are lack of English fluency, cognitive impairment, or concurrent major degenerative conditions likely to cause functional deterioration. Two members of the research team who are radiation oncologists (IP, Sunnybrook, and JR, Princess Margaret) will review patients scheduled for follow-up at their respective HNC clinics for eligibility, and will approach those who are eligible to ask if they are interested in learning more about a rehabilitation research project. Those who express interest will be connected with an on-site research assistant, who will provide the potential participant with additional information about the study and to answer any questions they may have. If the survivor is willing, the research assistant will obtain informed consent and schedule an assessment and alpha RC intervention time. The research assistant will provide the participant with the Brief Rehabilitation Assessment for Head and Neck Cancer Survivors (BRASH) for the patient to review and complete prior to meeting with the Rehabilitation Consultant. We anticipate that we will be able to recruit 1 participant per week.

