2.4.1.2 Procedures. Participants will be required to attend 3-4 sessions that are a combination of face-to-face visits and telephone calls. Session 1: Face-to-face, at the research site (either Sunnybrook or Princess Margaret) a research assistant will conduct a pre-intervention *research* assessment (approximately 60 minutes) and then on the same day, a rehabilitation consultant, licensed physiotherapist [name], will administer the face-to-face phase of alpha-RC *intervention* (approximately 90 minutes). Session 2: As a second phase of the alpha-RC *intervention* process, the rehabilitation consultant (CD) will conduct a telephone follow-up with the participant (45 to 60 minutes). Session 3: Within one week of Session 2, the participant will complete a post-intervention *research* assessment with the research assistant (approximately 60 minutes), either as a face-to-face visit at the research site, or as a telephone interview. For Session 3, it will be the participant's choice to have either a face-to-face or telephone interview, based on what is most convenient for him or her. This

choice has been put in place because many patients travel to Sunnybrook and Princess Margaret from out-of-region to receive specialized treatment for head and neck cancer, making an additional face-to-face visit very inconvenient for some. It is possible that, as part of the alpha-RC *intervention*, participants will require a second follow-up session that may occur as a second telephone call or a second face-to-face meeting. This is expected to happen rarely. The rehabilitation consultant will log any additional follow-up meetings, including type (phone or face-to-face), reason for meeting, outcome of meeting, next steps.

Participants will be remunerated \$25 for each *research* visit to the site to offset their transportation and parking costs, for a total of \$50 per participant. Additional *intervention-only* visits will not have any remuneration.

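### Step 6 aims at an intervention-effect estimate that a single-group pilot cannot give, and plans its effect sizes without confidence intervals

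*Combined protocol and SAP*

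**What the plan says.** Section 2.6 (Step 6, Pilot Testing) plans a mixed-method study with one group, a convenience sample of about 35. It takes its eligibility from section 2.4.1: "adult survivors of HNC who have completed active treatment (surgery, radiation, chemotherapy or any combination thereof) within the last year". The purpose includes "a pilot outcome evaluation to estimate the impact of the beta-RC on function and quality of life".

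On analysis it says: "Quantitative data analysis will be exploratory and descriptive", and in the same sentence "effect sizes will be calculated for all outcomes to help plan for a future, controlled trial". For normally distributed data, "We will calculate means, standard deviations, and Cohen's" *d* are planned. For other data the plan is medians, ranges and a nonparametric *r* computed from z and N.

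At the end of the section, the results are expected to inform feasibility, to help choose primary and secondary outcomes for a later controlled trial, and to "provide data to calculate sample size to ensure an adequately powered trial".

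There are three research assessments. Session 1 is before the intervention. For Session 3, section 2.4.1.2 says: "Within one week of Session 2, the participant will complete a post-intervention" research assessment. The third is added in Step 6: "Session 4 will occur 1-2 months after Session 3".

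The text gives no confidence interval for *d* or *r*. It does not name the standardising SD for *d*, or the test and count behind z and N. It does not say that within-group change is not the effect of the RC.

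**The concern.** An aim of estimating impact is causal, and it needs some view of what would have happened without the RC. One group measured before and after has none. Participants have finished surgery, radiation or chemotherapy within the past year, so scores could well move without the RC. Regression to the mean and other care act on the same change and cannot be separated from it.

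This matters because the effect sizes have a stated use beyond description, namely planning a controlled trial. A colleague who took the pilot *d* as an estimate of the RC effect could size that trial wrongly in either direction. With no interval beside it, *d* would also look more precise than about 35 people allow. The pilot's own descriptive results are not affected.

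**Working it through.** **1. The plan's own figure.** The only figure is the sample of about 35. No alpha, power, SD, effect size or precision target is attached to it, so there is nothing to reproduce, and the figure is not disputed here. Everything in steps 3 to 6 is illustration on assumed values. The documents give no *d*, SD, correlation or amount of change without the RC.

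**2. Timing of the assessments.** Table 3 places the follow-up session 2 to 10 weeks after the consultation, and Session 3 comes within a week of it. With a single follow-up session:
- Session 1 to Session 3: 2 to 10 weeks plus 0 to 1 week = 2 to 11 weeks.
- Session 1 to Session 4: a further 1 to 2 months (4.3 to 8.7 weeks) = about 6 to 20 weeks.

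Both intervals allow recovery that has nothing to do with the RC, and they differ between participants.

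**3. If *d* were read as the RC effect.** Take a two-arm trial compared by t-test, two-sided 5%, 80% power, SD = 1. The normal approximation is n per arm = 2(1.960 + 0.842)² / d².
- d = 0.5: 15.7 / 0.25 = 62.8, or 64 per arm with the t correction.
- d = 0.3: 15.7 / 0.09 = 174.4, or 176 per arm with the t correction.

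Suppose the observed *d* is 0.5 but the true RC effect is 0.3. At 64 per arm the noncentrality is 0.3 × √(64/2) = 1.70, against a critical t of about 1.98 on 126 degrees of freedom. Power is 39%.

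The error can run the other way. If the true effect were 0.3 and the observed *d* 0.2, the trial would be set at 394 per arm, and 394 / 176 = 2.2 times the need.

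**4. Imprecision at n = 35.** For a paired *d* (mean change divided by the SD of change), t = d√n. Inverting the noncentral t on 34 degrees of freedom gives these 95% intervals:

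| Observed paired *d* | 95% interval |
|---|---|
| 0.3 | −0.04 to 0.64 |
| 0.5 | 0.15 to 0.85 |
| 0.8 | 0.41 to 1.18 |

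Reporting an interval does not narrow it, but it shows the reader how little the point estimate settles.

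**5. Why the denominator should be named.** With equal SDs at the two times, *d* on the change-score SD = *d* on the baseline SD / √(2(1 − r)), where r is the pre-post correlation. A change of 0.4 baseline SD becomes 0.40, 0.52 or 0.63 at an assumed correlation of 0.5, 0.7 or 0.8. A reader given only *d* cannot convert between these scales.

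**6. The same gap for the nonparametric *r*.** Since r = z/√N, z = 2.5 gives 2.5/√35 = 0.42 if N counts people and 2.5/√70 = 0.30 if N counts observations.

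**The case against.** The strongest reply is that the harm needs a step the documents do not take. A reader might infer from the planning purpose that the pilot *d* will be entered as the controlled trial's target difference. Section 2.6 does not say so. It says the results will supply data for a sample-size calculation, and the planned means and SDs are legitimate inputs for that. Effect sizes across all outcomes can also help choose the later trial's outcomes, a use that needs no causal reading. This stands, and it makes mis-sizing a risk only.

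Second, the analysis is labelled exploratory and descriptive, the study is openly single-group, and a controlled comparison is left to later work. That lowers the weight of the point. It does not remove it, because neither the label nor the single-group description says that within-group change is not the RC effect, and the stated aim says the reverse.

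Third, a reader might infer that the contrast for *d* is wholly open. It is not. Sessions 1 and 3 are labelled as before and after the intervention, and Session 4 is an added follow-up, so the natural contrasts are Session 1 to 3 and Session 1 to 4. Naming them, and the SD, fills in missing detail and corrects no error.

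Fourth, imprecision at this size is a feature of any small pilot. True, and no larger sample is asked for. The request is only that the imprecision be shown.

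**Conclusion.** The point holds, at minor severity. The design cannot support the stated aim of estimating the RC's impact, and effect sizes intended for planning are to be reported without intervals. That conclusion rests on the text and on the absence of a control group, not on any assumed number.

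The size of any consequence is not known from the documents. The 39% power at 64 per arm, against 176 per arm needed, describes one assumed case (observed 0.5, true 0.3). It also requires the later team to adopt the pilot *d* as its target, which the documents neither plan nor rule out. It should not be read as an expected loss.

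**What to change.** In section 2.6:

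1. Replace the aim of estimating the impact of the beta-RC with one of describing change after it.
2. Report each effect size for Session 1 to 3 and for Session 1 to 4, with a 95% confidence interval. State the standardising SD for *d*, and the test and the N behind z for *r*. Report the baseline SD, change-score SD and pre-post correlation alongside.
3. State that within-group effect sizes are not estimates of the RC effect and will not be used as the controlled trial's target difference. For sizing, the pilot would supply SDs, correlation, recruitment and retention.

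The cost is protocol wording and a few extra descriptive statistics, with no added patients or visits. The downside is that the planning figures may look less favourable, and the target difference must be justified from another source. That justification belongs to the design of the later trial, not to this protocol.
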